17.2 Safety Review Board (SRB)

The SRB will oversee the progress of the study and determine whether the criteria to dose-escalate have been met at each stage. The SRB will consist of independent clinicians/scientists/statisticians who are not involved in the study. Investigators responsible for the clinical care of volunteers or representative of the Sponsor may not be a member of the SRB. Details of membership, chair and co-chair and responsibilities are outlined in the SRB charter. Principal Investigator(s) or designee and/or a Sponsor representative may be asked to join an open session of the SRB meeting to provide information on study conduct, present data or to respond to questions. Safety data will be reviewed by the SRB at pre-specified time points and at an ad-hoc basis.

17.2.1 Timing and content of Interim Safety Reviews

Interim safety reviews will be conducted by the SRB at the following times:

- Once all volunteers in Group A have been followed for at least 42 days after injection
- Once all volunteers in Group B have been followed for at least 42 days after injection
- Once all volunteers in Group C have been followed for at least 56 days after injection
- Once all volunteers in Group D have been followed for at least 56 days after injection

The SRB will be asked to review the following unblinded data at the planned interim reviews. Data will include all accumulated safety data available at the time:

- Summary of reactogenicity (i.e., solicited adverse events)
- All clinical adverse events judged by the Principal Investigator or designee to be possibly, probably or definitely related to the IMP and all pIMD
- All laboratory adverse events confirmed on retest and judged by the Principal Investigator or designee to be possibly, probably, or definitely related to IMP and/or clinically significant
- Summary of ECG findings. The SRB will be provided copies of specific ECGs if they request.
- Summary of cardiac troponin I results. The SRB will be provided individual cardiac troponin I results if they request.
- All SAEs
- PG9 antibody level (for Group C review only, to determine if higher dose is indicated or if enrolment should be expanded to C1)

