SAFETY MONITORING AND STATISTICAL CONSIDERATIONS	All clinical trial data collected, identified only by a study identification number, will be entered into a database. Safety will be continually monitored by the Investigators, the Sponsor's Medical Monitor and a Protocol Safety Review Team (PSRT); detailed stopping criteria are pre- defined. All safety data will be reviewed by an independent Safety Review Board (SRB). Ad-hoc safety review may be specifically requested by the Sponsor, the Principal Investigators, Ethics Committees, Regulatory Authorities, or by the SRB. At the end of the study, a full analysis will be prepared according to a pre-specified statistical analysis plan. All clinical and routine laboratory data will be included in the safety analysis. Antibody and immunogenicity analyses will be performed according to a predefined analysis plan for all volunteers who received IMP or placebo.

TABLE OF CONTENTS

ABB	REVIATIONS	11
CON	TACT INFORMATION	12
1.0	SIGNATURE PAGE	14
2.0	INTRODUCTION AND BACKGROUND INFORMATION	
2. 2.3 2.4 2.5	Experience with recombinant AAV vectors	17 17 19 20 21 21 22 22 23
3.2	Secondary Objectives	23
4.0	STUDY ENDPOINTS	24
	Study Endpoints	24
5.0	STUDY DESIGN	24
5.1 5.2 5.3 5.4 5.5	Study Population Inclusion Criteria Exclusion Criteria	27 27 27
6.0	STUDY VISITS	30
6.1 6.2 6.3 6.4 6.5 6.6	Injection Visit Post-Injection Visits Additional Follow-up Visits Unscheduled Visits	31 32 32 32
7.0	STUDY PROCEDURES	33
7.1 7.2 7.3 7.4 7.4 7.5 7.6	Medical History and Physical Examination HIV Testing and HIV Test Counselling HIV Risk Reduction Counselling Contraception Counselling Specimens.	33 34 34 34 34

 7.7 Randomization and Blinding 7.8 Unblinding Procedure for Individual Volunteers 7.9 Referral to Long Term Follow-Up Study 	

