*Vasculitis: Vasculitis, Diffuse vasculitis, leucocytoclastic vasculitis, polyarteritis nodosa, microscopic polyangiitis,Wegener's granulomatosis, anti-neutrophil cytoplasmic antibody positive vasculitis, Henoch-schönlein purpura, allergic granulomatous angiitis (Churg-Strauss disease), Kawasaki disease, Takayasu's arteritis, temporal arteritis (giant cell arteritis), renal vasculitis.

Medical judgement should be exercised in deciding whether other disorders/diseases have an autoimmune origin and should also be reported as described above, and this judgement is the investigator's prerogative. Whenever sufficient data exist to substantiate any of the diagnoses in the above list, the event must be reported as a pIMD. While the intent of pIMD reporting is to be inclusive, isolated nonspecific symptoms, which might (or might not) represent the above diagnoses, should be captured as AEs but not reported as pIMDs until the diagnosis can be defended.

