17.2.2 Criteria for Dose Escalation

The following criteria must be met to proceed to the next dose level:

- No new ECG findings suggestive of cardiac disease
- No confirmed and clinically significant elevated cardiac troponin I levels
- No case of a disease that might be immune mediated and is judged to be possibly, probably or definitely related to IMP, such as acute arthritis, severe generalized rash, or glomerulonephritis
- No pattern of reactogenicity or adverse events suggestive of autoimmune disease or immune mediated disease
- No serious adverse event which is assessed as probably or definitely related to the IMP
- No volunteer death which is assessed as possibly, probably or definitely related to the IMP

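### The listed SRB package screens unsolicited, non-serious, non-pIMD clinical AEs by the blinded investigator's causality rating, although the synopsis promises all safety data and the pattern criterion for escalation has no such limit

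*Protocol*

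**What the plan says.** Section 17.2.1 introduces the package with "The SRB will be asked to review the following unblinded data at the planned interim reviews", followed by "Data will include all accumulated safety data available at the time". The list then contains:

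- solicited events: "Summary of reactogenicity (i.e., solicited adverse events";
- clinical AEs: "All clinical adverse events judged by the Principal Investigator or designee to be possibly, probably or definitely related to the IMP and all pIMD";
- laboratory AEs confirmed on retest and judged "possibly, probably, or definitely related to IMP and/or clinically significant";
- ECG and troponin I summaries;
- all SAEs;
- PG9 level, at the Group C review only.

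The synopsis (safety monitoring row) says: "All safety data will be reviewed by an independent Safety Review Board (SRB".

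Among the escalation criteria in section 17.2.2 is: "No pattern of reactogenicity or adverse events suggestive of autoimmune disease or immune mediated disease". The criterion just before it, on single cases of possibly immune-mediated disease, does require a judgement of relatedness. This one does not.

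Section 10.5 says that "isolated nonspecific symptoms, which might (or might not) represent the above diagnoses, should be captured as AEs but not reported as pIMDs" until a diagnosis can be defended. Section 10.3 gives the causality rating to the Principal Investigator or designee, and section 7.7 blinds the investigator to active or placebo, though not to dose group.

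**The concern.** The SRB is the only body for which the protocol plans unblinded safety review. It alone is placed to notice that events which looked unremarkable one at a time fall mainly in active recipients. The pattern criterion asks for that kind of judgement across events. One class of clinical event, however, is passed to the SRB only after a blinded investigator has rated it related, so the reading across events starts from a list already narrowed by case-by-case attribution.

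The class matters for this product. Section 2.7 names immune-mediated disease (hepatitis, nephritis, vasculitis, arthritis) as the feared systemic harm. Its first signs may be mild and nonspecific. One consideration for attribution in section 10.3 is whether the event follows a known response pattern of the product, and section 2.4 states that there is no human experience with it.

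**Working it through.** No power or rate calculation applies. The check is to take each kind of event and ask whether 17.2.1 sends it to the SRB without regard to attribution.

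| Kind of event | Listed regardless of attribution? |
|---|---|
| Solicited local and systemic events | Yes, as a summary |
| SAEs | Yes |
| pIMD | Yes |
| Laboratory AEs confirmed on retest and clinically significant | Yes |
| ECG and troponin I findings | Yes, as summaries |
| Unsolicited, non-serious, non-pIMD clinical AEs | **No: only if rated at least possibly related** |

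The gap is the last row. Next, can an early immune-mediated symptom fall into it?

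1. **Content of the solicited list.** Section 9.1.2 solicits fever, chills, headache, nausea, vomiting, malaise and myalgia. Section 9.1.1 solicits injection-site signs. Arthralgia and generalised rash are on neither list.
2. **Timing.** Reactogenicity is assessed on the injection day and at Days 3 and 7 (section 6.3, Appendix A). Section 2.7 puts peak expression as early as 4 weeks and says the review interval was chosen to capture events after that peak. Taking Day 7 as the end of solicitation, 42 − 7 = 35 of the first 42 days (Groups A and B) and 56 − 7 = 49 of the first 56 days (Groups C and D) have no solicited collection. In that time symptoms enter only as unsolicited AEs.
3. **The pIMD route.** Section 10.5 keeps isolated nonspecific symptoms as ordinary AEs until a diagnosis can be defended.
4. **Result.** A non-serious arthralgia at Day 30 rated unlikely is not solicited, not an SAE, not a pIMD and not rated related. No listed clinical AE entry carries it.

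Do other safeguards in the protocol catch it?

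- Every pausing criterion in section 17.4 requires a judgement of relatedness.
- The sentinel rule in section 5.0 does too.
- The Protocol Safety Review Team (section 17.1) reviews clinical safety data weekly during the injection phase with no stated causality limit, but it is not described as unblinded.

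Scale: with four volunteers per group (3 active, 1 placebo), the reviews after Groups A, B, C and D cover 4, 8, 12 and 16 volunteers cumulatively. If the trial goes to C1, only the first three take place. With three active recipients at a dose level, two unlisted events in different active recipients would be 2/3 = 67% of that level's exposed volunteers.

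The second primary endpoint (section 4.1.1) counts moderate or greater unsolicited AEs through Day 168 with no attribution condition. The listed package can therefore omit events that count towards a primary endpoint.

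**The case against.** Several points against this stand.

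- **The SRB is far from limited to related events.** A reader might infer from the clinical AE entry that it sees nothing else. The same entry adds every pIMD, and the list adds all SAEs, all solicited events in summary, and the cardiac summaries.
- **The laboratory route is open.** Section 2.7 uses CRP, creatine kinase, urinalysis, and renal and liver tests as screens for immune-mediated disease, and section 9.1.10 adds C3 and C4. A confirmed, clinically significant abnormality reaches the SRB without being rated related. It would carry the laboratory finding, though, and not the symptom.
- **Section 5.0 is not a clear contradiction.** It speaks of all safety data available but attaches the dose groups in brackets, so it can mean cumulative across groups. The lead-in of 17.2.1 can be read the same way, or as entitling the SRB to everything. Only the synopsis sentence plainly conflicts with the list.
- **The threshold for a possible relationship is low, and ad hoc review exists.** Section 17.2 allows the SRB to meet ad hoc and to put questions to the investigator or sponsor. The SRB charter is not shown and may define a fuller package.

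It is also tempting to put a probability on the loss. Suppose a truly product-caused event is rated at least possible with probability s between 0.5 and 0.8, independently across events. Both of two such events would then be listed with probability s² = 0.25 to 0.64, and at least one with probability 1 − (1 − s)² = 0.75 to 0.96. The protocol gives no value for s, and ratings by the same investigators are unlikely to be independent. These figures are illustrative only and the point does not rest on them.

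**Conclusion.** The point holds for one class: unsolicited, non-serious, non-pIMD clinical AEs rated unlikely or not related. For that class the list in 17.2.1 conflicts with the synopsis, fits poorly with its own lead-in, and leaves out inputs that the pattern criterion in 17.2.2 calls for. Nothing else in the protocol gives an unblinded body those events as a matter of routine.

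A reader might go further and conclude that the pattern criterion cannot be applied at all. The documents do not support that. The SRB can still judge patterns across related AEs, solicited events, pIMDs, SAEs and clinically significant laboratory findings, and can ask for more. The criterion is under-supplied but still usable.

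The size is qualitative: one event class at up to four reviews. The conclusion assumes that the list in 17.2.1 describes what is actually delivered; a charter that already requires a full AE listing would reduce this to a wording correction. The point is worth correcting because the change is cheap, but it does not invalidate the escalation scheme.

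**What to change.** Change the second bullet of 17.2.1 to: *All clinical adverse events irrespective of investigator attribution, listed by dose group and unblinded arm with severity and attribution shown, and all pIMD.* The attribution stays visible to the SRB but no longer decides what it sees.

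Leave the laboratory bullet as written, since confirmed, clinically significant results already pass without attribution. Because that bullet still selects, have the synopsis sentence refer to 17.2.1 for the content of the package, and state whether the lead-in of 17.2.1 means cumulative across dose groups. Align the SRB charter.

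The cost is one protocol edit with its cross-references, the charter alignment, and a slightly longer listing for 4 to 16 volunteers cumulatively. The data coordinating centre drops a filter. No dose, escalation criterion or pausing rule changes.

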5.0 STUDY DESIGN

The study is a Phase 1 randomized, placebo-controlled, double-blind, dose-escalation clinical trial in healthy male adult volunteers to evaluate the safety and expression of a single intramuscular administration of rAAV1-PG9DP at $4x10^{12}vg$, $4x10^{13}vg$, $8x10^{13}vg$ and $1.2x10^{14}vg$.

Sentinel recipients

The rAAV1-PG9DP administrations escalate by dosage as shown below in Table 1, Study Design. In Groups A-D, the first 3 volunteer injections will be separated by 7 days, to allow for observation of IMP-related adverse events in the first two participants. Because there is one placebo in each group, the first two recipients will be treated as sentinel recipients (at least one will receive the IMP). If no reactogenicity and adverse events that are considered to be related to IMP (possibly, probably or definitely related) and are graded as severe or worse (Grade 3 or 4 on the DAIDS Toxicity Table) occur within 7 days after injection, the second volunteer may be injected. The same process will be followed after the second injection. If no events meeting the criteria described above occur within 7 days after the second volunteer is injected, then the

above do occur for the first two volunteers, they will be reviewed by the Safety Review Board (SRB) to determine whether further injections may proceed.

Dose escalation

Once all volunteers in the first dosage group (Group A) have received their injection, enrolment into the next higher dosage group / assignment of new allocation numbers will pause. Safety data through the Day 42 post-injection visit for all volunteers in the dosage group will be reviewed by the SRB prior to allowing volunteers into the second dosage group (Group B). Specific safety criteria to allow dose escalation are detailed in Section 17.2.2. If criteria for dose escalation are met, Group B enrolment will proceed. Once safety data through Day 42 post-injection visit is available for all volunteers in Group B, all available safety data (Groups A and B) will be reviewed by the SRB prior to allowing volunteers into Group C. If criteria for dose escalation are met, Group C enrolment will proceed. Once safety data through Day 56 post-injection visit is available for all volunteers in Group C, all available safety data (Groups A, B and C) will be reviewed by the SRB. In addition, PG9 antibody expression will be evaluated.

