7.5 Specimens

Approximately 40mL of blood will be collected at the Screening Visit and up to approximately 90mL of blood will be collected at later visits, usually from the antecubital fossa.

Muscle tissue biopsy will be collected from all volunteers in group D1 at 3 months and 12 months after administration of IMP at one of the six sites where the IMP was injected into the quadriceps.

All specimens will be handled according to the procedures specified in instructions provided by the Sponsor.

In the event of an abnormal laboratory value, volunteers may be asked to have a repeat/ additional sample collected at the discretion of the Principal Investigator or designee.

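### The SRB's planned-review list takes laboratory adverse events only when confirmed on retest, yet the retest is discretionary and 'confirmed' is undefined; this conflicts with the promise that the SRB sees all safety data

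*Protocol*

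**What the plan says.** Section 17.2.1 sets out what the SRB is asked to review, unblinded, before each escalation. Its laboratory line covers "All laboratory adverse events confirmed on retest and judged by the Principal Investigator or designee" to be at least possibly related to product and/or clinically significant. Troponin has a separate line: "Summary of cardiac troponin I results. The SRB will be provided individual cardiac troponin I results if they request".

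On repeat sampling, section 7.5 says that after an abnormal value "volunteers may be asked to have a repeat/ additional sample collected at the discretion of the Principal Investigator or designee". No time limit is given.

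On the scope of SRB data, the lead-in to the 17.2.1 list says "Data will include all accumulated safety data available at the time". Section 5.0 says "all available safety data (Groups A and B) will be reviewed by the SRB prior to allowing volunteers into Group C", with parallel wording for the later reviews, and the Synopsis (Safety Monitoring and Statistical Considerations) gives the SRB all safety data without qualification.

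Section 17.2.2 uses the idea of confirmation in one of its six escalation criteria: "No confirmed and clinically significant elevated cardiac troponin I levels".

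**The concern.** A filter that depends on an optional action is not a neutral filter. Whether a laboratory event appears on the SRB's list turns partly on whether somebody chose to draw a second sample, and a missing repeat can only shorten the list. Section 2.7 relies on creatine kinase, C-reactive protein, renal and liver tests and urinalysis to screen for immune-mediated disease, and 17.2.2 asks the SRB to judge whether there is a pattern of events suggesting it. Isolated, unrepeated values are part of the material for that judgement.

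Each cohort behind an escalation decision (Groups A to D) has three active recipients and one placebo recipient, so one omitted volunteer is a large share of the evidence.

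**Working it through.** **1. Which lines of the 17.2.1 list carry a retest condition?**

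| Line | Retest condition |
|---|---|
| Reactogenicity summary | none |
| Related clinical adverse events, and all pIMDs | none |
| Laboratory adverse events, related and/or clinically significant | confirmed on retest |
| ECG summary | none |
| Troponin I summary | none |
| All SAEs | none |
| PG9 level (Group C review only) | not applicable |

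Only the laboratory adverse event line is filtered. Set against the all-safety-data statements in the Synopsis, in 5.0 and in the list's own lead-in, it is narrower than what is promised.

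**2. Is a retest required anywhere?** Section 7.5 makes it discretionary. Section 10.6 has adverse events followed until they resolve or stabilise, or to the end of the study, and 10.3 calls for medically indicated diagnostic methods. Neither requires a repeat before an SRB review, and no section says whether the next scheduled sample counts as the retest.

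**3. What other routes reach the SRB?** Section 10.1 counts abnormal laboratory findings as adverse events, so the 17.4 pausing criteria apply to them.
- A related Grade 3 or 4 event goes to the SRB without confirmation.
- A related Grade 2 event lasting more than 7 days also goes. For a laboratory value, though, persistence can be shown only by another sample.
- SAEs and pIMDs go without a retest condition.

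What remains exposed, among non-troponin events never repeated, is Grade 1 events and Grade 2 events not shown to last beyond 7 days, when judged related or clinically significant, plus Grade 3 or 4 events judged unrelated but clinically significant.

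**4. When is a later scheduled panel least likely?** Per Appendix A and 9.1.10, safety laboratories are weekly from Day 7 to Day 42, and Days 49 and 70 are troponin only.
- Groups A and B close at Day 42. The next full panel is Day 56: 56 − 42 = 14 days later.
- Groups C and D close at Day 56. The next full panel is Day 84: 84 − 56 = 28 days later.

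Section 5.0 separates the first three injections by 7 days. Assume that minimum spacing, the fourth volunteer dosed with the third, and a review held as soon as the last volunteer closes. The first volunteer is then 7 + 7 = 14 days ahead. In Groups A and B he is at Day 42 + 14 = 56 and may have another full panel; the last-dosed volunteers do not. In Groups C and D he is at Day 56 + 14 = 70, a troponin-only visit, so nobody in the cohort has a full panel after Day 56. Longer spacing or a later review narrows this.

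**5. Scale.** Section 14.2 gives an exact 95% upper bound of 70.8% for no events in three active recipients. It reproduces: 1 − 0.025^(1/3) = 0.708. With one event in three, the bound p solves (1 − p)³ + 3p(1 − p)² = 0.025, giving p = 0.906. Leaving out one affected active recipient therefore turns 1/3 (upper bound 90.6%) into 0/3 (upper bound 70.8%). This shows what one omission could do, not how likely it is.

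**6. Troponin.** The list filter does not touch it, because its summary has no retest condition. The gap is in 17.2.2, which requires confirmation without saying how an unrepeated elevation is classed. Appendix B gives troponin I only a Grade 4 entry, for levels consistent with infarction or unstable angina. A lesser rise therefore has no tabulated grade and would not clearly meet the first pausing criterion.

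**The case against.** The strongest reply is that the SRB is not confined to this list. The lead-in promises all accumulated safety data; SAEs, pIMDs, ECG and troponin have unfiltered lines; and 17.4 brings related Grade 3 or 4 events to the SRB, normally within 2 business days. Weekly sampling to Day 42 means most abnormal values are followed by another sample. The SRB is independent and unblinded, can ask for individual troponin values, and works under a charter that is not shown.

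Much of this stands, and it rules out some stronger readings that a reader might infer:
- *No laboratory event reaches the SRB without a retest.* The routes above contradict this.
- *An unrepeated value passes the escalation criteria.* Confirmation appears in one of six criteria, for troponin I, whose results the SRB sees unfiltered. The filtered line and the confirmed criterion concern different values. How an unrepeated troponin value is classed is not stated, so treating it as not confirmed is an inference.
- *A transient rise would be gone by the next visit.* The protocol gives no marker kinetics, and whether a later value falls below a limit depends on the size of the initial rise.
- *The list is defective because it is narrower than the second primary endpoint.* The two serve different purposes and would differ without any retest wording; the clinical line is also restricted by relatedness.

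The reply does not remove the contradiction. The all-data sentence introduces the very list that contains the filter, so staff assembling the report could follow either. Weekly sampling does not cover the closing visit.

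**Conclusion.** The point holds as an internal inconsistency with a bounded safety consequence. Sections 7.5 and 17.2.1 together allow a related or clinically significant non-troponin laboratory event to be missing from the SRB's list because nobody repeated it, contrary to the Synopsis, 5.0 and the list's own lead-in. The exposure is limited to the event types in step 3 of the working and is greatest for values first seen at the closing visit. Separately, 17.2.2 leaves the status of an unrepeated troponin elevation open.

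This rests on reading the laboratory line as written and on no other document settling the matter. The frequency of such omissions cannot be estimated from the protocol, and nothing here shows that an escalation decision would have been different. It merits correction because cohorts are small, the product is first-in-human, and the remedy is cheap.

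**What to change.** In 17.2.1, remove confirmation on retest as a condition for listing. Give the SRB a per-volunteer listing of laboratory adverse events and elevated troponin I values, each with its retest status: confirmed, not confirmed, or not retested. State what counts as elevated for troponin I, and how C-reactive protein, C3 and C4 enter the listing, since Appendix B has no row for them.

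Define *confirmed*, including whether the next scheduled sample qualifies. The sponsor should then reconcile 7.5, 17.2.1 and 17.2.2 on how an unrepeated value is reported and treated; that choice is clinical and belongs to the sponsor and the SRB.

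The cost is wording in the protocol and the SRB report template, and slightly longer listings for about four volunteers per review.
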